Serum creatinine OR Measured or calculated ^b creatinine clearance (CrCl) (GFR can also be used in place of creatinine or CrCl)	≤1.5 X upper limit of normal (ULN) OR ≥50 mL/min for subject with creatinine levels > 1.5 X institutional ULN
Hepatic	
Serum total bilirubin	≤ 1.5 X ULN OR Direct bilirubin ≤ ULN for subjects with total bilirubin levels > 1.5 ULN
AST (SGOT) and ALT (SGPT)	≤2.5 X ULN OR ≤5 X ULN if liver metastases are present
Coagulation	
International Normalized Ratio (INR) or Prothrombin Time (PT)	≤1.5 X ULN unless subject is receiving anticoagulant therapy as long as PT or INR is within therapeutic range of intended use of anticoagulants
Activated Partial Thromboplastin Time (aPTT)	≤1.5 X ULN unless subject is receiving anticoagulant therapy as long as aPTT is within therapeutic range of intended use of anticoagulants

^a ANC, Platelets and Hemoglobin requirements cannot be met by use of recent transfusion or growth factor support (G-CSF, erythropoietin, etc) within 2 weeks prior to treatment initiation

^b Creatinine clearance should be calculated per institutional standard.

7. Male subjects should agree to use an adequate method of contraception starting with the first dose of study therapy through 120 days (approximately 4 months) after the last dose of study therapy.

5.1.3 *Subject Exclusion Criteria*

The subject must be excluded from participating in the trial if the subject:

1. Received more than 2 prior systemic treatment regimens with chemotherapy, targeted therapy, radiopharmaceuticals, or immunotherapy in the metastatic setting or received more than 1 prior chemotherapeutic regimen in the metastatic setting.
2. Is currently participating and receiving study therapy or has participated in a study of an investigational agent and received study therapy or used an investigational device within 4 weeks of the first dose of treatment.
3. Has a diagnosis of immunodeficiency or is receiving any systemic steroid therapy, abiraterone acetate, other androgen synthesis inhibitors or any form of immunosuppressive therapy within 7 days prior to Day 1 of trial treatment. The use of physiologic doses of corticosteroids may be approved after consultation with the Sponsor.
4. Has had a prior monoclonal antibody or autologous cellular immunotherapy within 4 weeks prior to study Day 1 or who has not recovered (i.e., \leq Grade 1 or at baseline) from AEs due to agents administered more than 4 weeks earlier.

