5.2.1.2.2 ADXS31-142

The most likely anticipated AEs associated with ADXS31-142 are comprised primarily of individual flu-like symptoms (e.g., fatigue, lethargy and low grade fever) or cytokine release symptoms (e.g., constitutional symptoms such as fever, chills, rigors, headache, nausea, vomiting, tachycardia, shortness of breath, hypotension, and rash). These symptoms usually present within 2-4 hours after the completion of infusion and are often mild to moderate and transient in nature or respond quickly to symptomatic treatment. In rare instances, they may last up to 24 hours. No cumulative or delayed toxicity has been observed.

Less likely AE's include increase heart rate, low blood pressure, muscle aches, headaches, allergic reaction, changes in blood chemistry, changes in blood counts, and short term changes in liver function.

Rare but serious AEs include high fever, difficulty breathing and hypotension.

██████████ ADXS31-142 has a tropism for the liver. Transient asymptomatic elevations of ALT and alkaline phosphatase were observed after dosing with ADXS11-001 in the Phase 1 trial without prophylactic medication administration. For that reason, subjects with significant liver disease are excluded, and particular attention is to be paid to hepatic abnormalities.

The dose of ADXS31-142 will not be modified (e.g., reduced or increased) unless if it is determined that the toxicities are clearly attributed to ADXS31-142 or the combination, the treatment modification guidelines for drug-related AEs in [Table 9](#) shown below are to be followed.

Table 9 Treatment Delay/Discontinuation Guidelines for Drug-Related Adverse Events-ADXS31-142

Toxicity	Grade	Hold treatment	Timing for restarting treatment	Discontinue treatment
Hematologic	1-3	No	N/A	N/A
	4	Yes	Toxicity resolves to ≤Grade 1 or baseline	Toxicity does not resolve to ≤Grade 1 or baseline within 12 weeks
Non-hematologic, excluding cytokine release symptoms and DLTs	1	No	N/A	N/A
	2-3	Yes	Toxicity resolves to ≤Grade 1	Toxicity not resolved to ≤Grade 1 within 12 weeks of last infusion ^a
	4	N/A	Permanently discontinue treatment	Permanently discontinue treatment

^a With Investigator and Sponsor agreement, subjects with a non-heme AE (e.g., alopecia, neuropathy) still at grade 2 after 12 weeks, may continue treatment if only asymptomatic and controlled.

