5.5 Concomitant Medications/Vaccinations (Allowed & Prohibited)

Medications or vaccinations specifically prohibited in the exclusion criteria are not allowed during the ongoing trial. If there is a clinical indication for one of these or other medications or

vaccinations specifically prohibited during the trial, discontinuation from trial therapy or vaccination may be required. The Investigator should discuss any questions regarding this with the Sponsor. The final decision on any supportive therapy or vaccination rests with the Investigator and/or the subject's primary physician. However, the decision to continue the subject on trial therapy or vaccination schedule requires the mutual agreement of the Investigator, the Sponsor, and the subject.

5.5.1 *Acceptable Concomitant Medication*

All treatments that the Investigator considers necessary for a subject's welfare may be administered at the discretion of the Investigator in keeping with the community standards of medical care. All concomitant medication and therapies will be recorded in the electronic case report form (eCRF) including all prescription, over-the-counter (OTC), herbal supplements, and IV medications and fluids. If changes occur during the trial period, documentation of drug dosage, frequency, route, and date should also be included on the CRF.

All concomitant medications received within 28 days before informed consent is signed and through the 30-Day Follow-Up period should be recorded in the eCRF. Concomitant medications administered to treat SAEs and ECIs should be recorded as defined in [Section 7.2](#)

5.5.2 *Prohibited Concomitant Medications*

Subjects are prohibited from receiving the following therapies during the Screening and Treatment Phase (including retreatment for post-complete response relapse) of this trial:

- Anti-cancer therapy including but not limited to hormonal, chemotherapy, radiation therapy, and treatment with targeting agents (e.g., tyrosine kinase inhibitors). However, occasional therapy for palliation of pain is allowed. Note: Radiation therapy to a symptomatic soft tissue lesion, bone lesions or to the brain may be allowed after consultation with Sponsor. Radiopharmaceuticals (radium, strontium, etc.) are not acceptable.
- Immunotherapy not specified in this protocol; unless approved by Investigator and Sponsor
- Bisphosphonates and denosumab

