 - Note: Subjects already being treated with bisphosphonates or denosumab may continue treatment, however, introduction of either is not allowed while on study.
- Investigational agents other than ADXS31-142 and pembrolizumab (MK-3475)
- PI3K and TNF α inhibitors
- Live vaccines within 30 days prior to the first dose of trial treatment and while participating in the trial. Examples of live vaccines include, but are not limited to, the following: measles, mumps, rubella, chicken pox, yellow fever, rabies, *Bacille Calmette-*

Guerin (BCG), and typhoid (oral) vaccine. Seasonal influenza vaccines for injection are generally killed virus vaccines and are allowed; however intranasal influenza vaccines (e.g., Flu-Mist®) are live attenuated vaccines, and are not allowed.

- Systemic glucocorticoids for any purpose other than to modulate symptoms from an event of clinical interest of suspected immunologic etiology or to manage cytokine release symptoms. The use of physiologic doses of corticosteroids may be approved after consultation with the Sponsor. Intermittent use of inhaled steroids is allowed for management of asthma.
- Anti-infectives should be avoided. Note: Subjects with a documented infectious complication should receive oral or IV antibiotics or other anti-infective agents as considered appropriate by the treating Investigator for a given infectious condition, according to standard institutional practice.
- Acetaminophen is not to be used for pre-medication because it does not have anti-inflammatory properties required for AE amelioration but may be used for supportive care measures; for subjects where naproxen and ibuprofen are contraindicated, an alternative anti-inflammatory should be used. Sponsor consultation is recommended.

Subjects who, in the assessment of the Investigator, require the use of any of the aforementioned treatments for clinical management should be removed from the trial. Subjects may receive other medications that the Investigator deems to be medically necessary.

The Exclusion Criteria describe other medications that are prohibited in this trial.

There are no prohibited therapies during the Post-Treatment Follow-up Phase.

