5.6 Rescue Medications & Supportive Care

5.6.1 *Supportive Care Guidelines*

Subjects should receive appropriate supportive care measures as deemed necessary by the treating Investigator. Suggested supportive care measures for the management of AEs with potential immunologic etiology are outlined below. Where appropriate, these measures include the use of oral or intravenous treatment with corticosteroids as well as additional anti-inflammatory agents if symptoms do not improve with administration of corticosteroids. Note that several courses of steroid tapering may be necessary as symptoms may worsen when the steroid dose is decreased. For each disorder, attempts should be made to rule out other causes such as metastatic disease or bacterial or viral infection, which might require additional supportive care. The treatment guidelines are intended to be applied when the investigator determines the events to be related to pembrolizumab (MK-3475) or ADXS31-142.

Note: If after evaluation, the event is determined not to be related, the Investigator does not need to follow the treatment guidance (as outlined below). Refer to [Section 5.2.1](#) for dose modification.

It may be necessary to perform conditional procedures such as bronchoscopy, endoscopy, or skin photography as part of evaluation of the event.

5.6.1.1 *Pneumonitis:*

- For **Grade 2 events**, treat with systemic corticosteroids. When symptoms improve to Grade 1 or less, steroid taper should be started and continued over no less than 4 weeks.
- For **Grade 3-4 events**, immediately treat with IV steroids. Administer additional anti-inflammatory measures, as needed.
- Add prophylactic antibiotics for opportunistic infections in the case of prolonged steroid administration.

5.6.1.2 *Diarrhea:*

Subjects should be carefully monitored for signs and symptoms of enterocolitis (such as diarrhea, abdominal pain, blood or mucus in stool, with or without fever) and of bowel perforation (such as peritoneal signs and ileus).

- All subjects who experience diarrhea should be advised to drink liberal quantities of clear fluids. If sufficient oral fluid intake is not feasible, fluid and electrolytes should be substituted via IV infusion. For Grade 2 or higher diarrhea, consider GI consultation and endoscopy to confirm or rule out colitis.
- For **Grade 2 diarrhea/colitis** that persists > than 3 days, administer oral corticosteroids.

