Additionally, any SAE, considered by an Investigator who is a qualified physician, to be related to the Advaxis' or Merck's product that is brought to the attention of the Investigator at any time outside of the time period specified in the previous paragraph also must be reported immediately to inVentiv Health Clinical Pharmacovigilance (Attn: iHC SAE Reporting; [contact] or email: [contact]).

SAE reports and any other relevant safety information are to be forwarded to: inVentiv Health Clinical Pharmacovigilance (Attn: iHC SAE Reporting; [contact] or email: [contact]).

Adverse Event reports meeting the requirements of a 7 Day Reports, 15 Day Reports, or the requirements for inclusion in the Annual Periodic Reports will be submitted as required to FDA, European Union (EU), Pharmaceutical and Medical Devices agency (PMDA) or other local regulators. Investigators will be provided a copy of the submission and will utilize this for submission to local IRB/ECs as required. The submission will cross reference the Sponsor's Investigational Compound Number (IND, CSA, etc.).

All subjects with SAEs must be followed up for outcome.

7.2.3.2 *Events of Clinical Interest*

Selected non-serious and SAEs are also known as ECIs and must be reported to the Sponsor. ECIs must be recorded as such on the Adverse Event CRFs/worksheets and reported within 24 hours to inVentiv Health Clinical Pharmacovigilance (Attn: iHC SAE Reporting; [contact] or email: [contact]).

ECIs for this trial include:

1. Overdose, as defined in [Section 7.2.1 - Definition of an Overdose for This Protocol and Reporting of Overdose to the Sponsor](#), which is not associated with clinical symptoms or abnormal laboratory results.
2. An elevated AST or ALT value that is $\geq 3X$ the upper limit of normal and an elevated total bilirubin value that is $\geq 2X$ the upper limit of normal and, at the same time, an alkaline phosphatase value that is $\leq 2X$ the upper limit of normal, as determined by way of protocol-specified laboratory testing or unscheduled laboratory testing.*
3. Cytokine release syndrome (CRS): Subjects presenting with all 6 symptoms of CRS that include nausea, headache, tachycardia, hypotension, rash, and shortness of breath.
4. Listeremia
5. Hypotension – \geq Grade 2
6. Any AE \geq Grade 3

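### Table 9 lets ADXS31-142 restart at Grade 1 or less with no steroid limit, the same grade at which section 5.6.1 suggests starting a steroid taper of at least 4 weeks

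*Combined protocol and SAP*

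**What the plan says.** - **Restart rule.** For Grade 2-3 non-hematologic toxicity, with DLTs and cytokine release symptoms excluded, the restart column of Table 9 asks only that "Toxicity resolves to ≤Grade 1". The discontinuation column gives 12 weeks from the last infusion. Neither column mentions steroids. The table is invoked "if it is determined that the toxicities are clearly attributed to ADXS31-142 or the combination".
- **Taper.** Section 5.6.1.1 (pneumonitis, Grade 2) reads: "When symptoms improve to Grade 1 or less, steroid taper should be started and continued over no less than 4 weeks". Similar wording appears for diarrhea/colitis, hypophysitis, Grade 3-4 hyperthyroidism, hepatic events and renal events (5.6.1.2 and 5.6.1.4 to 5.6.1.7). Section 5.6.1 presents these measures as suggestions and sends the reader to section 5.2.1 for dose modification, which contains Table 9.
- **Steroids at entry and on study.** Exclusion criterion 3 covers systemic steroids and "any form of immunosuppressive therapy within 7 days prior to Day 1 of trial treatment". Section 5.5 adds: "Medications or vaccinations specifically prohibited in the exclusion criteria are not allowed during the ongoing trial". Section 5.5.2 then prohibits "Systemic glucocorticoids for any purpose other than to modulate symptoms from an event of clinical interest of suspected immunologic etiology"; treatment of cytokine release is the other exception. Subjects who "require the use of any of the aforementioned treatments for clinical management should be removed from the trial". Section 7.2.3.2 counts every adverse event of Grade 3 or higher as an event of clinical interest (ECI).
- **Pembrolizumab.** For several toxicities, Table 8 discontinues if steroids cannot be brought to 10 mg/day prednisone-equivalent within 12 weeks. Its restart column, like that of Table 9, refers to grade alone.

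**The concern.** Grade 1 or less is both the point at which the vector may be given again and the point at which the suggested taper begins. On that day the subject may be on the full therapeutic steroid dose. A clinician who follows Table 9 as written can therefore infuse live bacteria during therapeutic immunosuppression, which exclusion criterion 3 was meant to avoid at first dosing.

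The issue is subject safety and consistency between sections. It changes no sample size, error rate or planned estimate. A careless repair, however, could alter the DLT count that drives the Part B dose decision.

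**Working it through.** The plan gives no figure on this point to reproduce. The check follows the rules through and then counts days.

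**1. Grade 3 colitis after the DLT window, attributed to the combination.** The window closes one week after dose 2, on Day 22 + 7 = 29.
- If the event persists beyond a week, 5.6.1.2 suggests IV and then high-dose oral steroids, with the taper from Grade 1.
- The event is Grade 3, so it is an ECI. With suspected immunologic etiology it falls within the exemption in 5.5.2.
- Table 8 (colitis, Grade 2-3) restarts pembrolizumab at Grade 0-1. Table 9 restarts ADXS31-142 at Grade 1 or less.
- Re-dosing near the start of a high-dose taper therefore complies with both tables and with 5.5.2.

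**2. Grade 2 events.** These are generally not ECIs. Read literally, 5.5.2 removes a subject who needs steroids for one, yet Tables 8 and 9 provide for restart after Grade 2. The documents do not settle which prevails. Before dose 2 the point concerns mainly Grade 2 events, because most related Grade 3 non-hematologic events in the window are DLTs and fall outside this row.

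**3. Other controls.** The note to Table 15 requires laboratory values within the Table 3 limits before each dose of trial treatment. That holds ADXS31-142 for out-of-range hepatic, renal or blood-count values whatever the attribution, but it contains no steroid limit. For a non-laboratory event attributed to pembrolizumab alone, no stated rule holds ADXS31-142.

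**4. Calendar.** Doses fall on Days 1, 22 and 43, and the next cycle starts on Day 85 (5.2.2). The gaps are 21, 21 and 42 days. The minimum taper is 28 days, so any taper begun in a 21-day gap is still running on the next dose day. Over the 84-day cycle, 70 of 84 possible start days give a taper containing a scheduled dose (69 to 71, depending on endpoints).

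Over 24 months (730 days) there are 9 × 3 = 27 doses and 26 gaps: 18 of 21 days and 8 of 42 days. Only the first gap and 7 days of the second lie in the DLT window.

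**5. Therapeutic overlap.** The documents give no steroid dose. Assume a linear 28-day taper from D0 mg/day starting on Day s.
- Dose on Day d = D0 × (1 − (d − s)/28).
- Days to reach 10 mg/day: t = 28 × (1 − 10/D0).
- Delay under a 10 mg rule when dose 2 is due on Day 22: s + t − 22, rounded up.
- Second dose more than 14 days late when s > 36 − t.

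| D0 (assumed) | t (days) | Starts on Days 2-22 still above 10 mg on Day 22 | Above 10 mg on Day 85 | Delay if s = 15 | Dose 2 more than 14 days late |
|---|---|---|---|---|---|
| 20 | 14 | Days 9-22 (14 of 21) | s ≥ 72 | 7 days | no start up to Day 22 |
| 40 | 21 | Days 2-22 (21 of 21) | s ≥ 65 | 14 days | s ≥ 16 |
| 60 | 23.3 | Days 2-22 (21 of 21) | s ≥ 62 | 17 days | s ≥ 13 |
| 80 | 24.5 | Days 2-22 (21 of 21) | s ≥ 61 | 18 days | s ≥ 12 |

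The overlap and delay columns apply equally to every later 21-day gap. If toxicity has already pushed a dose past its due date, Table 9 permits it on the first day of the taper. The added wait under a 10 mg rule is then t itself, 14 to 25 days rounded up.

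**6. Knock-on for DLTs.** Section 5.2.1.1.1 makes a delay of more than 2 weeks to the second dose, if due to treatment-related toxicity, a DLT. The 17- and 18-day delays in the table exceed that. A bare steroid limit could turn a Grade 2 event that is not a DLT now into one.

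**The case against.** The strongest reply is that Table 9 should not be read alone. Section 5.5 carries the entry restriction on steroids into the trial and makes continued treatment depend on agreement between investigator, sponsor and subject. The pre-dose laboratory check applies to every dose. Table 8 lets physicians hold study medication for intolerable or persistent Grade 2 events, and its own restart column has no steroid condition. Table 10 even adds 50 mg hydrocortisone as premedication, so steroid exposure at infusion is not always treated as a bar.

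The biological risk is also tempered. The vector is attenuated and lacks the gene for cell-to-cell spread, it is cleared by knock-out mice lacking adaptive immunity (9.4.2), and oral antibiotics start about 72 hours after each infusion.

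Much of this stands, and it lowers the risk. It does not close the gap. Agreement without a threshold gives no guidance on dose, the laboratory check does not see a steroid, and one premedication dose differs from a taper of 4 weeks or more. The protocol itself still warns of delayed listeremia (5.6.1.10).

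A reader might go further and infer that nothing holds ADXS31-142 when pembrolizumab is blamed. The Table 15 note refutes that for hepatic, renal and blood-count abnormalities. A reader might also infer that the protocol directs dosing under steroids. It permits this, and the taper is only suggested care. Finally, 70 of 84 and 21 of 21 are counts of calendar days, not risks to subjects.

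**Conclusion.** The gap is real and should be corrected. For Grade 3 immune-related events after the DLT window, the written rules allow a live-vector infusion during high-dose steroid treatment, and only an agreement clause without a threshold stands in the way. For Grade 2 events the rules conflict.

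Overlap with a taper of the minimum length is certain in any 21-day gap if doses are given on schedule. How much of it is therapeutic dosing depends on the assumed 20-80 mg/day start and linear shape. No event incidence is given, so the number of affected subjects cannot be estimated, and the documents do not support a claim that listeriosis will follow.

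Confidence is medium: section 5.2.3 has no text in this copy, and the Pharmacy Manual, which covers administration, was not available.

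**What to change.** 1. Add to the Table 9 restart column that total systemic corticosteroid must be no more than 10 mg/day prednisone-equivalent, excepting the Table 10 hydrocortisone premedication and sponsor-approved physiologic replacement. The figure is borrowed from a Table 8 discontinuation rule. The sponsor's clinicians may set a stricter limit in line with exclusion criterion 3.
2. Apply the condition to ADXS31-142 whichever drug the event is attributed to.
3. State that a delay due only to this condition, once toxicity is at Grade 1 or less, does not count toward the 2-week or missed-second-dose DLT criteria. Otherwise the new hold could affect the modified 3+3 decision and, at Dose Level -1, end a subject's treatment.
4. Stop ADXS31-142 if the steroid limit is not reached within 12 weeks, as in Table 8, and say from when the 12 weeks run.

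The cost is a short amendment and some later doses: 7 to 18 days for the taper starting on Day 15, and up to 25 days where toxicity has already postponed the dose. Some subjects would also stop who could now restart. If the 84 days run from the last infusion, Grade 1 must be reached by day 84 − t: day 70, 63, 60 or 59 (rounded down) for the four assumed starting doses.

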5.2.1.1.1 Dose Limiting Toxicity Criteria

The same DLT criteria will be utilized for study Part A and Part B. All toxicities will be graded using CTCAE v 4.03. The DLT window of observation will begin at the administration of the initial dose of ADXS31-142 and end 1 week following the second dose of ADXS31-142. The occurrence of any of the following toxicities will be considered a DLT, if judged by the investigator to be possibly, probably or definitely related to study treatment administration. Treatment modifications for DLT are shown in Table 8 and Table 9.

General:

1. Prolonged delay (>2 weeks) in initiating the second dose due to treatment-related toxicity
2. Missing the second dose of ADXS31-142 or pembrolizumab (MK-3475) as a result of AE(s) during the first cycle.

Hematologic:

1. Grade 4 hematologic toxicity.
2. Febrile neutropenia, defined as absolute neutrophil count (ANC) $< 1000/\text{mm}^3$ with a single temperature of >38.3 degrees C (101 degrees F) or a sustained temperature of ≥ 38 degrees C (100.4 degrees F) for more than 1 hour.
3. Grade 3 thrombocytopenia lasting >72 hours.
4. Grade 4 thrombocytopenia.

Non-Hematologic:

1. \geq Grade 3 non-hematologic toxicity, (excluding nausea, vomiting and/or diarrhea lasting <3 days and reversible with medical intervention).
2. Grade 3 non-hematologic laboratory value that does not downgrade to Grade 2 within 3 days after onset of the event despite optimal medical management (excluding transient Grade 3 laboratory value abnormalities reversible within 5 days and without medical intervention).
3. Listeremia: positive blood culture(s) along with persistent (for 72 hours post dose) symptoms consistent with listeremia (e.g., fever and muscle aches, often preceded by diarrhea or other gastrointestinal symptoms).
4. \geq Grade 3 flu-like or cytokine release symptoms that persist for >24 hours after ADXS31-142 administration despite symptomatic treatment (Refer to Section 7.2.3.2).

Subjects who experience a DLT at Dose Level -1 of 0.5×10^9 will be discontinued from study treatment. However, subjects who experience a DLT at DL 1 of 1×10^9 may be eligible to receive ADXS31-142 at a lower dose level for subsequent doses and cycles following discussion and agreement between the Investigator and Sponsor.

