- For **Grade 3 or 4 diarrhea/colitis** that persists > 1 week, treat with IV steroids followed by high dose oral steroids.
- When symptoms improve to Grade 1 or less, steroid taper should be started and continued over no less than 4 weeks.

5.6.1.3 *Diabetes:*

Type 1 diabetes mellitus (T1DM) (if new onset, including diabetic ketoacidosis [DKA]) or \geq Grade 3 hyperglycemia, if associated with ketosis (ketonuria) or metabolic acidosis (DKA)

- For **T1DM or Grade 3-4 Hyperglycemia**
 - Insulin replacement therapy is recommended for T1DM and for Grade 3-4 hyperglycemia associated with metabolic acidosis or ketonuria.

- Evaluate subjects with serum glucose and a metabolic panel, urine ketones, glycosylated hemoglobin, and C-peptide.

5.6.1.4 *Hypophysitis:*

- For **Grade 2** events, treat with corticosteroids. When symptoms improve to Grade 1 or less, steroid taper should be started and continued over no less than 4 weeks. Replacement of appropriate hormones may be required as the steroid dose is tapered.
- For **Grade 3-4** events, treat with an initial dose of IV corticosteroids followed by oral corticosteroids. When symptoms improve to Grade 1 or less, steroid taper should be started and continued over no less than 4 weeks. Replacement of appropriate hormones may be required as the steroid dose is tapered.

5.6.1.5 *Hyperthyroidism or Hypothyroidism:*

Thyroid disorders can occur at any time during treatment. Monitor subjects for changes in thyroid function (at the start of treatment, periodically during treatment, and as indicated based on clinical evaluation) and for clinical signs and symptoms of thyroid disorders.

- **Grade 2** hyperthyroidism events (and **Grade 3-4** hypothyroidism):
 - In hyperthyroidism, non-selective beta-blockers (e.g., propranolol) are suggested as initial therapy.
 - In hypothyroidism, thyroid hormone replacement therapy, with levothyroxine or liothyronine, is indicated per standard of care.
- **Grade 3-4** hyperthyroidism
 - Treat with an initial dose of IV corticosteroid followed by oral corticosteroids. When symptoms improve to Grade 1 or less, steroid taper should be started and continued over no less than 4 weeks. Replacement of appropriate hormones may be required as the steroid dose is tapered.

5.6.1.6 *Hepatic:*

- For **Grade 2** events, monitor liver function tests more frequently until values return to baseline (consider weekly).
 - Treat with IV or oral corticosteroids

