*Note: These criteria are based upon available regulatory guidance documents. The purpose of the criteria is to specify a threshold of abnormal hepatic tests that may require an additional evaluation for an underlying etiology.

ECIs that occur in any subject from the date of first dose through 30 days following cessation of treatment, or the initiation of a new anticancer therapy, whichever is earlier, must be reported within 24 hours of awareness to inVentiv Health Clinical Pharmacovigilance (Attn: iHC SAE Reporting; [contact] or email: [contact]).

7.2.4 *Evaluating Adverse Events*

An Investigator who is a qualified physician will evaluate all AEs according to the CTCAE v 4.03. Any AE that changes CTCAE grade over the course of a given episode will have each change of grade recorded on the AE CRFs according to [Table 16](#). All AEs regardless of CTCAE grade must also be evaluated for seriousness. Symptoms associated with Cytokine Release Syndrome (CRS) which include *nausea, headache, tachycardia, hypotension, rash, and shortness of breath* MUST be reported as individual symptoms. If a subject manifest all five CRS symptoms, then CRS can be reported as a single event. Otherwise they must be reported individually as it is not a true CRS.

Table 16 Evaluating Adverse Events

V4.03 CTCAE Grading	Grade 1	Mild; asymptomatic or mild symptoms; clinical or diagnostic observations only; intervention not indicated.
	Grade 2	Moderate; minimal, local or noninvasive intervention indicated; limiting age-appropriate instrumental ADL.
	Grade 3	Severe or medically significant but not immediately life-threatening; hospitalization or prolongation of hospitalization indicated; disabling; limiting self-care ADL.
	Grade 4	Life threatening consequences; urgent intervention indicated.
	Grade 5	Death related to AE
Seriousness	A SAE is any AE occurring at any dose or during any use of Advaxis or Merck product that:	
	† Results in death; or	
	† Is life threatening; or places the subject, in the view of the investigator, at immediate risk of death from the event as it occurred (Note: This does not include an AE that, had it occurred in a more severe form, might have caused death.); or	
	† Results in a persistent or significant disability/incapacity (substantial disruption of one's ability to conduct normal life functions); or	

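### For diarrhea/colitis, the suggested steroid start is later at Grade 3-4 (more than 1 week) than at Grade 2 (more than 3 days)

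*Combined protocol and SAP*

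**What the plan says.** Section 5.6.1.2 sets two steroid triggers for treatment-related diarrhea/colitis. At Grade 2, the event is one "that persists > than 3 days, administer oral corticosteroids". At Grade 3 or 4, it is one "that persists > 1 week, treat with IV steroids followed by high dose oral steroids". The bullet before these, on GI consultation and endoscopy, covers Grade 2 and above; the first steroid bullet names Grade 2 only.

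The opening of Section 5.6.1 sets the status of this text: "Suggested supportive care measures for the management of AEs with potential immunologic etiology are outlined below". It leaves supportive care to the treating investigator's judgment and adds: "For each disorder, attempts should be made to rule out other causes such as metastatic disease or bacterial or viral infection".

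Section 5.5.2 prohibits systemic glucocorticoids in general but allows them to "modulate symptoms from an event of clinical interest of suspected immunologic etiology" or to manage cytokine release symptoms. Section 7.2.3.2 makes every adverse event of Grade 3 or above an event of clinical interest.

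In Section 5.2.1.1.1, the first non-hematologic DLT criterion counts toxicity of Grade 3 or worse, "excluding nausea, vomiting and/or diarrhea lasting <3 days and reversible with medical intervention".

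**The concern.** Steroid timing runs against severity. A site that follows the two bullets as written would start steroids sooner for a moderate colitis than for a severe or life-threatening one. The documents give no reason for the week.

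What is at stake is patient safety, not inference. The default matters because sites will consult this section when such an event occurs. Section 5.2.1.1.2 says Part A is completed, so the text now bears mainly on Part B. There every subject is to receive pembrolizumab together with ADXS31-142, and Section 5.2.1.1.3 plans about 30 subjects at the recommended dose.

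**Working it through.** The plan has no statistical figure to reproduce here. The check is a comparison of text with one subtraction.

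**1. Size of the gap.** Inputs, both from 5.6.1.2: Grade 2 trigger, more than 3 days; Grade 3-4 trigger, more than 1 week, that is, more than 7 days. Difference: 7 - 3 = 4 days.

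**2. Who meets the gap.** A subject with more than 3 days at Grade 2 before worsening already has oral steroids suggested. The full 4 days apply to events that start at Grade 3 or 4, or that spend no more than 3 days at Grade 2. So 4 days is a maximum.

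**3. The other steroid entries in 5.6.1.1 to 5.6.1.7.**

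| Entry | Steroids at Grade 2 | Steroids at Grade 3-4 |
|---|---|---|
| Pneumonitis (5.6.1.1) | no wait | immediate, IV |
| Diarrhea/colitis (5.6.1.2) | after >3 days, oral | after >1 week, IV then oral |
| Hypophysitis (5.6.1.4) | no wait | no wait, IV then oral |
| Hyperthyroidism (5.6.1.5) | none suggested | no wait, IV then oral |
| Hepatic (5.6.1.6) | no wait | no wait, IV |
| Renal (5.6.1.7) | no wait | no wait, systemic |

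The diabetes entry (5.6.1.3) suggests no steroids. Diarrhea/colitis is the only entry with a wait at either grade, and its wait is longer at the higher grade.

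**4. Is an earlier Grade 3-4 trigger given elsewhere?** No. Table 8 holds pembrolizumab at Grade 2-3 and stops it at Grade 4. Table 9 has a similar hold and stop rule for ADXS31-142, outside DLTs. Neither sets a steroid start for diarrhea/colitis.

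**5. Would an earlier start disturb the DLT rule?** The exclusion in 5.2.1.1.1 needs a duration under 3 days and reversal with medical intervention, and it has no upper grade limit.

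- Grade 3, steroids after more than 3 days: the event has already outlasted the exclusion, so a steroid start at that trigger cannot change its DLT status.
- Grade 4, no fixed wait: steroids could start inside the 3-day window and reverse the event, so that a would-be DLT becomes an excluded one. Part of this is caught already. Table 8 stops pembrolizumab at Grade 4, and missing the second dose because of an adverse event is itself a DLT. But the window runs to 1 week after the second dose, and an event in that last week is not caught this way.

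**The case against.** The strongest reply is that no delay is required. The measures are suggested, the investigator decides, and Sections 5.5.2 and 7.2.3.2 together permit earlier steroids for a Grade 3 or 4 event of suspected immunologic origin. Other protection is in place: fluids, monitoring for perforation, GI consultation and endoscopy to be considered from Grade 2, the drug hold and stop rules, and reporting within 24 hours of any event of Grade 3 or above. All of this stands and lowers the weight of the point. None of it supplies an earlier written trigger.

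A second reply is that the week may be deliberate. The DLT criteria describe listeremia symptoms as "often preceded by diarrhea or other gastrointestinal symptoms", and the Grade 3-4 treatment is the more immunosuppressive one. The caution is fair. But the documents link listeriosis to diarrhea in general, not to its grade, and they already accept steroids after 3 days at Grade 2. They do not show whether the week is intended or a slip.

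Three stronger readings are tempting and not supported:

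- A reader might take Table 16's Grade 4 wording, "Life threatening consequences; urgent intervention indicated", as setting a time for steroids. It is a generic grade definition and names no treatment.
- A reader might set the 1-2 days for culture growth in 5.6.1.9 against the week and call the rest needless. That assumes a culture at onset, which the plan does not schedule. The same section says a negative culture does not exclude infection under strong suspicion.
- A reader might infer that the protocol withholds steroids for a week. It does not.

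**Conclusion.** The inversion is real and worth correcting, as a safety wording point of moderate weight. On the written default, steroids for Grade 3-4 diarrhea/colitis start up to 4 days later than for Grade 2. This assumes that a week means 7 days and that both durations run from the same starting point; the text does not say whether the clock starts at onset or on reaching the grade. The current bullet changes no endpoint or analysis. The documents give no diarrhea/colitis rate, so the number of subjects affected cannot be estimated.

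The documents also fix no correct threshold. More than 3 days at Grade 3 is the smallest change that removes the inversion. No fixed wait at Grade 4 is a judgment, consistent with how 5.6.1.1 handles Grade 3-4 pneumonitis.

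**What to change.** In 5.6.1.2, replace the one-week condition in the Grade 3-4 bullet with one rule per grade:

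- Grade 3: IV steroids, then high-dose oral, starting no later than the Grade 2 trigger (more than 3 days).
- Grade 4: the same treatment with no fixed waiting period.
- Both: after the infection rule-out that 5.6.1 already asks for, stating that it includes listeremia. Leave the choice of tests to the investigator.

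In 5.2.1.1.1, add that Grade 4 diarrhea needing IV steroids is not covered by the exclusion for diarrhea of under 3 days. Earlier steroids then cannot remove a DLT.

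The cost is one bullet of guidance and one clause in the DLT rule, with no new scheduled procedure. The clinical downside is that some infectious or self-limiting events may receive steroids earlier, with a taper of at least 4 weeks, in subjects given a live Listeria product. The rule-out step and the 3-day allowance at Grade 3 limit this risk but do not remove it. If the sponsor intends the week, the alternative is to state the reason for it in 5.6.1.2.
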